6.0 TREATMENT PLAN

This study is a single-center, open-label randomized pilot study of lower-dose vs higher-dose G-CLAM for medically less fit adults with newly diagnosed AML or analogous myeloid neoplasms at the Fred Hutchinson Cancer Research Center/University of Washington/Seattle Cancer Care Alliance.

Study Overview

In this pilot study, patients meeting the inclusion/exclusion criteria and their primary oncologists are asked whether or not they would agree to participate in the randomized treatment assignment (APPENDIX D). Patients agreeable to randomization will be assigned in a 1:1 ratio to the higher-dose G-CLAM arm or the lower-dose G-CLAM arm that utilizes lower doses of cladribine, cytarabine, and mitoxantrone. For those who wish to not be randomized, the reasons to decline randomization will be recorded, and patients will be allowed to receive the treatment intensity of their choosing. Patients will receive higher-dose or lower-dose G-CLAM as follows:

Treatment arm	G-CSF (SC, D0-D5)	Cladribine (IV 2h, D1-D5)	Cytarabine (IV, D1-D5)	Mitoxantrone (IV, D1-D3)
Higher-dose G-CLAM	300 or 480 µg*	5 mg/m ²	2,000 mg/m ² **	18 mg/m ²
Lower-dose G-CLAM	300 or 480 µg*	2 mg/m ²	100 mg/m ² ***	6 mg/m ²

*Dosing based on patient weight: <76kg vs. ≥76 kg; **over 2 hours; ***over 1 hour

After study enrollment, patients will receive a first cycle of G-CLAM on one of the designated treatment arms. Post-induction bone marrows will be reassessed upon blood count recovery or between day Days +28 to +35 after start of chemotherapy, whichever occurs first. If a response other than a measurable (“minimal”) residual disease-negative (MRDneg) CR is achieved, the patient will receive re-induction with G-CLAM at the same dosing. Patients who achieve a morphologic CR or CR with incomplete count recovery (CRi) with up to 2 courses of higher-dose G-CLAM or up to 6 courses of lower-dose G-CLAM can receive consolidation therapy with G-CLA (i.e. mitoxantrone omitted; up to 4 cycles with high-dose G-CLA and up to 12 cycles of low-dose G-CLA).

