6.5 Assessment for Response after First Induction Course

A bone marrow aspirate should be obtained upon blood count recovery (i.e. ANC >1,000/µL and platelet count >100,000/µL) or between Days +28 to +35 after start of G-CLAM chemotherapy, whichever occurs first; a bone marrow biopsy need only be obtained during this procedure if spicules are absent from the aspirate sample.

- 6.5.1 Patients achieving an MRDneg CR: Patients are eligible to receive consolidation therapy with G-CLA (dosing as per section 6.6): up to 4 cycles on the high-dose arm and up to 12 cycles on the low-dose arm
- 6.5.2 Patients achieving a MRDpos CR or CRI: Patients are eligible for a second cycle of induction therapy using the same dosing guidelines as cycle 1 or may proceed to consolidation therapy with G-CLA as per 6.6, per discretion of treating attending.
- 6.5.3 Patients with persistent disease: Patients with persistent disease ($\geq 5\%$ blasts) are eligible for a second course of induction chemotherapy at the same dosing used in cycle 1 provided all non-hematologic toxicities have resolved to Grade <2. If they are not in CR or CRI after the 2nd induction course, they will be removed from the study.
- 6.5.4 Patients with persistent aplasia without evidence of disease after Day +49: patients will be removed from protocol.

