6.6 Consolidation Therapy

After achievement of a CR/CRI (irrespective of MRD) with 1-2 courses of G-CLAM therapy, patients are eligible for post-remission therapy with G-CLA.

- 6.6.1 The treatment is identical to the induction course but without mitoxantrone (i.e. G-CSF, cladribine, and cytarabine, or “G-CLA” at same dose level as induction). If a patient had excessive toxicities (grade ≥ 3 non-hematologic toxicity excluding neutropenic fever and infections) during induction, a dose reduction can be considered as described in sections 6.8 and 6.9, as well as APPENDIX B.
- 6.6.2 Post-remission courses should start within 6 weeks of achieving CR/CRI once patients have recovered to \leq Grade 2 toxicities from the previous course of therapy.
- 6.6.3 Patients on the higher-dose arm can receive up to 4 courses of consolidation therapy.
- 6.6.4 Patients on the lower-dose arm can receive up to 12 cycles of consolidation therapy.
- 6.6.5 Patients can proceed to transplantation barring contraindications and if a suitable donor is available.

6.7 **Monitoring during/after Induction and Consolidation Therapy**

For patient monitoring, the following studies and study intervals are suggested and will be performed at the physician's discretion:

- 6.7.1 Complete blood counts with differential blood count, including immature cells/blast, and platelet count at least 2 times weekly until ANC >500/ μ L and then at least weekly until platelet count >100,000/ μ L.
- 6.7.2 Metabolic panel, including bilirubin, ALT/AST, and creatinine at least weekly until ANC >1,000/ μ L and platelet count >100,000/ μ L.
- 6.7.3 If patients develop signs or symptoms suggestive of cardiac dysfunction, LVEF should be assessed using the same method to evaluate baseline LVEF status (MUGA scan or echocardiography, or other appropriate diagnostic modality).

6.8 **Dose Modifications of Chemotherapeutic Drugs for Induction or Subsequent Treatment Cycles for Higher-Dose Arm**

For patients who have organ dysfunction at baseline—defined as a serum creatinine > 2.0 mg/dL or a bilirubin concentration is $\geq 3 \times$ IULN— or those who experienced \geq Grade 3 non-hematologic toxicities excluding neutropenic fever and infections during the first induction, a dose reduction can be considered as follows (see also APPENDIX B):

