10.0 SUBJECT DISCONTINUATION OF ACTIVE TREATMENT

10.1 Criteria for Removal from Treatment

All reasons for discontinuation of treatment must be documented:

10.1.1 Completion of protocol treatment.

10.1.2 Arrival to the transplant service for planned HCT.

- 10.1.3** Initiation of any leukemia-directed therapy other than protocol therapy
- 10.1.4** Failure to achieve a CR or CRi after 2 courses of therapy with higher-dose G-CLAM or 6 courses of therapy with lower-dose G-CLAM.
- 10.1.5** Persistent aplasia (ANC <500/ μ L or platelets <50,000/ μ L) without evidence of leukemia after Day +49.
- 10.1.6** Relapse after achievement of CR/CRi during treatment.
- 10.1.7** Adverse toxicities that prevent continuation with study treatment.
- 10.1.8** Withdrawal of consent; the patient may withdraw from the study at any time for any reason.

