10.2 Duration of Follow-up

Patients will be followed after completion of study treatment to determine event free survival (EFS) and relapse-free survival ([RFS] (for patients achieving CR), as well as overall survival (for all patients) for a maximum of 5 years. Follow-up may include periodic (e.g. every 3 months) review of medical records, and, if absolutely necessary, direct contact of the study participant.

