14.3 Primary/Exploratory Endpoints/Hypotheses and Analytical Methods

14.3.1 Primary endpoint

The primary objective of this study is to evaluate the feasibility of randomizing patients to either intensive or non-intensive induction and post remission chemotherapy. We will consider randomization feasible (i.e. a subsequent, larger study would be designed as a randomized trial) if the true proportion of patients willing to be randomized is 60% or higher. With 50 patients in a feasibility study and accounting for the sample variation associated with 50 patients, we will consider randomization feasible if at least 52% of the patients agree to be randomized (i.e. 26 or more of 50 patients agree to be randomized). If the true proportion willing to be randomized is 60%, the probability of observing 52% or more willing to be randomized is 90%. The probability of having 26 or more of the 50 patients agree to be randomized is only 6% if the true randomization agreement rate is 40%, and <1% if the true randomization agreement rate is 30% or lower, providing good operating characteristics not only to avoid a false negative result but also a false positive result. If one treatment arm closes prematurely (see section on monitoring below), we will conclude that randomization is not feasible, and the remaining patients will be treated on the remaining arm. Continuation of enrollment into that remaining arm will allow us to gain additional experience and provide more precise estimates of treatment efficacy and treatment-related toxicities.

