14.4 Monitoring for efficacy and early mortality

This study will evaluate each regimen separately, and also compare regimens among patients who are randomized. Details for both sets of analyses are provided below.

Within-arm monitoring for efficacy and early mortality

We will enroll patients in 2 stages in order to allow for early stopping for unacceptable differences in early mortality or inefficacy. Early mortality will be defined as death for any reason on or before day 28 after starting therapy. Inefficacy will be evaluated using MRD^{neg} CR.

We will use our ongoing clinical trial using a CPX-351 in medically less fit adults with AML or high-grade MDS will provide “historical” control data for both inefficacy and early mortality. In this trial (FHCRC #2642.00), which used essentially identically inclusion/exclusion criteria, we have so far treated 37 subjects at a CPX-351 dose of 32 units/m². Among these, 8 patients achieved an MRD^{neg} CR (22%). Ten patients (27%) died within 28 days of treatment initiation; at least 4 of these subjects experienced early disease progression as main cause of death, highlighting the balance between treatment efficacy and potential toxicity.

In the first stage, 10 patients will be accrued to each arm, either in a randomized or non-randomized fashion. Each arm will be evaluated separately for early death and inefficacy stopping rules. Accrual may temporarily be held while outcome data on these patients matures.. As some patients may choose to not be randomized, the 2 treatment arms may be evaluated at a different time point for early stopping.

1) Lower-dose Arm: After 10 patients have been accrued to the lower-dose arm, we will evaluate for early death and inefficacy.

Early death: If the number of early deaths is 5 or higher, accrual will stop with the conclusion that the arm is too toxic for further randomization. If the true early mortality rate is 30% or less, the probability of observing 5 or more early mortality events is 15%.

Inefficacy: If there are 0 patients with MRD^{neg} CR, accrual will stop with the conclusion that the arm is not efficacious enough for further randomization. If the true MRD^{neg} CR rate is 22%, the probability of observing 0 MRD^{neg} CRs in 10 patients is 8%.

2) Higher-dose Arm: After 10 patients have been accrued to the higher dose arm, we will evaluate for early death and inefficacy.

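### Lower-dose G-CLAM induction stops at 2 courses under 6.5.3 and 6.6 but at 6 under 6.0 and 10.1.4

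*Combined protocol and SAP*

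**What the plan says.** Two sections of the combined protocol and SAP set the induction limit by arm. Section 6.0 (Treatment Plan, Study Overview) says that patients reaching CR or CRi with "up to 2 courses of higher-dose G-CLAM or up to 6 courses of lower-dose G-CLAM can receive consolidation therapy". Section 10.1.4 lists, as a reason for ending treatment, failure to reach CR or CRi after "2 courses of therapy with higher-dose G-CLAM or 6 courses of therapy with lower-dose G-CLAM".

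Two sections set a limit without naming an arm. Section 6.5.3 offers patients with persistent disease a second induction course and then states: "If they are not in CR or CRI after the 2nd induction course, they will be removed from the study". The opening sentence of 6.6 says that after CR/CRi "with 1-2 courses of G-CLAM therapy, patients are eligible for post-remission therapy with G-CLA".

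Three other provisions bear on the point:

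- Section 6.5.1 gives the consolidation limits as "up to 4 cycles on the high-dose arm and up to 12 cycles on the low-dose arm".
- Section 14.4 closes an arm with no MRD-negative CR among its first 10 patients: "accrual will stop with the conclusion that the arm is not efficacious enough for further randomization". It also compares MRD-negative CR between the arms by Fisher's exact test.
- Section 10.2 follows patients for "overall survival (for all patients) for a maximum of 5 years".

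**The concern.** A treating physician with a lower-dose patient not in remission after course 2 has two written instructions and cannot follow both. The same holds when a lower-dose patient first responds at course 3 or later and the question is whether consolidation may begin.

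The trial compares treatment intensity, so the number of courses an arm may deliver is part of what is being compared. If 6.5.3 is applied, lower-dose patients are cut off well short of the schedule in 10.1.4, while higher-dose patients keep their full allowance. If different sections are followed on different occasions, similar lower-dose patients receive different treatment, and either choice breaches a written rule.

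The limit also decides how long a lower-dose patient has in which to reach an MRD-negative CR, the response that 14.4 monitors.

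**Working it through.** **The plan's nearest figure.** The plan computes nothing from the course limit. The closest stated figure is the 8% chance in 14.4 of seeing no MRD-negative CR in 10 patients at a true rate of 22%. It reproduces: (1 − 0.22)^10 = 0.78^10 = 0.083. It is calculated at a fixed rate with no course number in it, so the conflict does not change it.

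**The limits side by side.**

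| Section | Names an arm? | Higher-dose limit | Lower-dose limit |
|---|---|---|---|
| 6.0 | yes | 2 | 6 |
| 10.1.4 | yes | 2 | 6 |
| 6.5.3 | no | 2 | 2 |
| 6.6, opening sentence | no | 2 | 2 |

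All four agree for the higher-dose arm. For the lower-dose arm they split two against two.

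**Can 6.5.3 and 6.6 be read as higher-dose rules only?** No. Section 6.5.1 sets a consolidation limit for each arm, and 6.6.3 and 6.6.4 do the same, so both sections cover both arms. The heading of 6.5 refers to the first induction course, but the disputed sentence expressly governs what follows the second. Nothing in the protocol says which section prevails.

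**Two lower-dose patients.**

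1. Persistent disease after course 2: removed under 6.5.3. Under 10.1.4, up to 6 − 2 = 4 more courses.
2. First CR/CRi at any of courses 3 to 6: may have consolidation under 6.0, but does not meet the condition in 6.6.

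**Dose at stake for patient 1.** Inputs are the lower-dose schedule in 6.4.1, with every dose given. Section 6.9 allows no reduction for toxicity in this arm.

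| Drug | Per course (mg/m²) | 2 courses | 6 courses |
|---|---|---|---|
| Mitoxantrone | 6 × 3 days = 18 | 36 | 108 |
| Cladribine | 2 × 5 days = 10 | 20 | 60 |
| Cytarabine | 100 × 5 days = 500 | 1,000 | 3,000 |

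The ratio is 2/6, one third, for each drug.

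**Which limit is likely intended?** Both sections that state the induction limit by arm give six. The consolidation limits are in the same proportion (12/4 = 3, and 6/2 = 3). That is suggestive only.

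**The case against.** Three objections have some force.

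First, inconsistent treatment may be rarer in practice than on paper. This is a single-center study, section 15.0 makes the principal investigator personally responsible for overseeing treatment, and 10.1 is the dedicated list of removal criteria, so many would follow it. That reduces the likely harm but leaves 6.5.3 in contradiction with it.

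Second, choosing six is an inference. It also removes the only text that would end lower-dose induction for non-response before course 6, which is a clinical decision in medically less fit patients and not mere tidying. This stands, so the limit should be confirmed before anything is edited.

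Third, a reader might infer that the conflict makes early closure of the lower-dose arm materially more likely and so threatens the primary conclusion, because 14.3.1 says: "If one treatment arm closes prematurely (see section on monitoring below), we will conclude that randomization is not feasible". The documents do not support that reading. It needs MRD-negative CRs that first appear at courses 3 to 6 in patients not in CR/CRi after course 2, and it needs 14.4 to count them. The documents give no lower-dose response rate by course, and 14.4 names no course or time window. The 22% reference rate comes from a CPX-351 trial (8 of 37), with no course count, and cannot be assigned to either two or six courses of lower-dose G-CLAM. The only timing data, in section 1.0, are from the earlier G-CLAM trial at the maximally tolerated dose: 3 patients needed 2 cycles to reach best response, against 52 who reached CR or CRp/i. Section 1.0 describes that trial's population as medically fit, and the dose was the higher one, so these data do not settle the matter either. The primary endpoint itself, agreement to be randomized, is recorded at enrollment and does not depend on the course limit. The effect on 14.4 is possible but cannot be sized.

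**Conclusion.** The contradiction is real, is confined to the lower-dose arm, and should be corrected. Applying 6.5.3 as written takes a lower-dose patient not in CR/CRi after course 2 off treatment at one third of the courses and cumulative dose that 10.1.4 permits. The dose figures assume full dosing and are upper limits for anyone who misses doses or stops for another reason.

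The lower-dose MRD-negative CR count in 14.4 could fall if late responses occur and are counted, but no probability should be attached to that. No sample size, power or alpha figure changes. That six is the intended limit is likely but not established by the text.

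**What to change.** The sponsor confirms the lower-dose induction limit. If it is six, amend as follows:

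- **6.5 heading:** retitle so that it covers response assessment after all induction courses.
- **6.5.2:** this has the same wording problem, offering MRD-positive CR or CRi patients only a second cycle whatever their arm. Allow further induction at the cycle 1 dosing up to a total of 2 higher-dose or 6 lower-dose courses, and keep the existing option to go to consolidation.
- **6.5.3:** use the same totals for persistent disease and keep the existing toxicity condition. State that patients not in CR or CRi after 2 higher-dose or 6 lower-dose courses are removed from treatment under 10.1.4, with follow-up continuing under 10.2. The removal should be from treatment and not from the study, because 10.2 follows all patients for survival.
- **6.6:** replace the 1-2 course condition with *up to 2 courses of higher-dose or up to 6 courses of lower-dose G-CLAM*.

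If the sponsor intends two courses, leave 6.5.3 and 6.6 at two and correct 6.0 and 10.1.4.

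The cost is wording. With six confirmed, there is no new procedure, visit or drug, no course beyond those 6.0 and 10.1.4 already allow, and no change to entry, randomization, stopping rules or sample size.

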6.6 Consolidation Therapy

After achievement of a CR/CRI (irrespective of MRD) with 1-2 courses of G-CLAM therapy, patients are eligible for post-remission therapy with G-CLA.

- 6.6.1 The treatment is identical to the induction course but without mitoxantrone (i.e. G-CSF, cladribine, and cytarabine, or “G-CLA” at same dose level as induction). If a patient had excessive toxicities (grade ≥ 3 non-hematologic toxicity excluding neutropenic fever and infections) during induction, a dose reduction can be considered as described in sections 6.8 and 6.9, as well as APPENDIX B.
- 6.6.2 Post-remission courses should start within 6 weeks of achieving CR/CRI once patients have recovered to \leq Grade 2 toxicities from the previous course of therapy.
- 6.6.3 Patients on the higher-dose arm can receive up to 4 courses of consolidation therapy.
- 6.6.4 Patients on the lower-dose arm can receive up to 12 cycles of consolidation therapy.
- 6.6.5 Patients can proceed to transplantation barring contraindications and if a suitable donor is available.

6.7 **Monitoring during/after Induction and Consolidation Therapy**

For patient monitoring, the following studies and study intervals are suggested and will be performed at the physician's discretion:

- 6.7.1 Complete blood counts with differential blood count, including immature cells/blast, and platelet count at least 2 times weekly until ANC >500/ μ L and then at least weekly until platelet count >100,000/ μ L.
- 6.7.2 Metabolic panel, including bilirubin, ALT/AST, and creatinine at least weekly until ANC >1,000/ μ L and platelet count >100,000/ μ L.
- 6.7.3 If patients develop signs or symptoms suggestive of cardiac dysfunction, LVEF should be assessed using the same method to evaluate baseline LVEF status (MUGA scan or echocardiography, or other appropriate diagnostic modality).

6.8 **Dose Modifications of Chemotherapeutic Drugs for Induction or Subsequent Treatment Cycles for Higher-Dose Arm**

For patients who have organ dysfunction at baseline—defined as a serum creatinine > 2.0 mg/dL or a bilirubin concentration is $\geq 3 \times$ IULN— or those who experienced \geq Grade 3 non-hematologic toxicities excluding neutropenic fever and infections during the first induction, a dose reduction can be considered as follows (see also APPENDIX B):

- 6.8.1 If a patient develops Grade ≥ 3 non-hematologic toxicity other than Grade 3 infections within 28 days from the last dose of G-CLAM, the next course of G-CLAM will be given once toxicity is \leq grade 2; doses for this course will be cladribine 4 mg/m² days 1-5, cytarabine 1,500mg/m² days 1-5, mitoxantrone 14 mg/m² days 1-3, and G-CSF dose unchanged. Assuming these doses are well-tolerated the first course of G-CLA will be administered at these doses, omitting mitoxantrone. If Grade ≥ 3 non-hematologic toxicity occurs again, there will be a further reduction in doses of cladribine to 3 mg/m² daily days 1-5 and cytarabine to 1,000mg/m² daily days 1-5 for the first cycle of G-CLA. Doses for subsequent courses of G-CLA will be discussed with the Principal Investigator.
- 6.8.2 Mitoxantrone: If the bilirubin concentration is $\geq 3 \times$ IULN, consider a dose reduction of mitoxantrone by 25-50% in consultation with the Oncology Pharmacist
- 6.8.3 Cladribine: If the serum creatinine exceeds 2.0 mg/dL and/or estimated creatinine clearance (calculated by Cockcroft-Gault) decreases to less than 50 mL/min during therapy, we will consider dose reduction in discussion with the Oncology Pharmacist.
- 6.8.4 Cytarabine: If the serum creatinine exceeds 2.0 mg/dL and/or estimated creatinine clearance (calculated by Cockcroft-Gault) decreases significantly during therapy, we will consider dose reduction in discussion with the Oncology Pharmacist.

6.9 **Dose Modifications of Chemotherapeutic Drugs for Subsequent Treatment Cycles for Low-Dose Arm**

Given the doses of the chemotherapy in this arm are already low, there will be no further dose reduction for toxicity. Also, doses do not need to be adjusted based on liver or kidney function. Decisions whether to proceed with further cycles of chemotherapy if \geq Grade 3 toxicity in cycle 1 will be made by the PI in conjunction with the treating physician.

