6.2 Pre-Treatment

At the discretion of the treating physician for clinical management only, allopurinol 300 mg PO daily (or equivalent dose adjusted for renal function) may be considered in all patients without known allergies to allopurinol to reduce the risk of tumor lysis. Higher doses of allopurinol are permitted if patients develop tumor lysis syndrome. Patients may receive rasburicase, a recombinant uric acid oxidase, for the prevention and/or treatment of tumor lysis syndrome at the discretion of the treating physician if clinically indicated. All patients should be adequately hydrated and receive anti-emetics as necessary.

6.3 Administration of G-CSF, Cladribine, and Cytarabine Mitoxantrone on the Higher-Dose Arm: INDUCTION

- 6.3.1** For induction: The doses of the elements of G-CLAM chemotherapy will be as follows G-CSF 300 or 480 μ cg/ (based on weight <76 kg vs. ≥ 76 kg) daily subcutaneously daily on Days 0-5, Cladribine 5 mg/m^2 IV daily over 2 hours on Days 1-5, Cytarabine 2,000 mg/m^2 IV daily over 2 hours on Days 1-5, and Mitoxantrone 18 mg/m^2 IV daily over 60 minutes on Days 1-3.
- 6.3.2** The doses of all medications are calculated using the patient's actual weight.
- 6.3.3** Days 0 and 1 G-CSF may be omitted at physician discretion for WBC $>20,000/\mu\text{L}$, signs/symptoms of leukostasis, or acute symptoms felt related to their high-grade myeloid neoplasm.
- 6.3.4** All treatment is given as intent-to-treat; missed doses will not be made up.

6.3.5 No investigational or commercial agents or therapies other than those described herein may be administered with the intent to treat the patient's malignancy.

6.3.6 **If the patient has significant organ-specific dysfunction at baseline (e.g. abnormal liver or kidney function), dose reduction can be considered as described in section 6.8 at the physician discretion in conjunction with the oncology pharmacist.**

Outline Treatment Schedule: Higher Dose G-CLAM	
Day	Treatment
0	G-CSF 300/480 μ cg
1	G-CSF, Cladribine 5 mg/m ² , Cytarabine 2,000 mg/m ² , Mitoxantrone 18 mg/m ²
2	G-CSF, Cladribine 5 mg/m ² , Cytarabine 2,000 mg/m ² , Mitoxantrone 18 mg/m ²
3	G-CSF, Cladribine 5 mg/m ² , Cytarabine 2,000 mg/m ² , Mitoxantrone 18 mg/m ²
4	G-CSF, Cladribine 5 mg/m ² , Cytarabine 2,000 mg/m ²
5	G-CSF, Cladribine 5 mg/m ² , Cytarabine 2,000 mg/m ²
28-35 OR blood count recovery	Bone marrow assessment

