APPENDIX B: DOSE MODIFICATION TABLE

For patients who experienced \geq Grade 3 non-hematologic toxicities excluding neutropenic fever and infections during the first induction, the following dose reduction can be considered for the next course

High-Dose Arm

Drug	Dose Reduction #1	Dose Reduction #2
G-CSF	No change	No change
Cladribine	Cladribine 4 mg/m ²	Cladribine 3 mg/m ²
Cytarabine	Cytarabine 1,500 mg/m ²	Cytarabine 1,000 mg/m ²
Mitoxantrone	Mitoxantrone 14 mg/m ²	NA

Low-Dose Arm

No dose reductions required.

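### Read literally, the fixed 14 mg/m² mitoxantrone dose that 6.8.1 sets after Grade ≥3 toxicity exceeds any first-course dose already reduced under 6.8.2, and the protocol does not say how the rules combine

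*Combined protocol and SAP*

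**What the plan says.** All references are to the combined protocol and SAP and concern the higher-dose arm.

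- **Starting dose (6.3.1).** Mitoxantrone is 18 mg/m² daily on days 1-3, cladribine 5 mg/m² and cytarabine 2,000 mg/m² daily on days 1-5.
- **Reduction at the first course (6.3.6).** For significant organ dysfunction at baseline, "dose reduction can be considered as described in section 6.8 at the physician discretion in conjunction with the oncology pharmacist".
- **Lead-in to 6.8.** The section opens "For patients who have organ dysfunction at baseline", which it defines as creatinine above 2.0 mg/dL or bilirubin at least 3 x IULN. It adds patients with Grade ≥3 non-hematologic toxicity in first induction. For both groups, "a dose reduction can be considered as follows (see also APPENDIX B".
- **Bilirubin rule (6.8.2).** At 3 x IULN or more, "consider a dose reduction of mitoxantrone by 25-50% in consultation with the Oncology Pharmacist".
- **Toxicity rule (6.8.1).** After Grade ≥3 non-hematologic toxicity, "doses for this course will be cladribine 4 mg/m² days 1-5, cytarabine 1,500mg/m² days 1-5, mitoxantrone 14 mg/m² days 1-3".
- **Renal rules (6.8.3, 6.8.4).** Reductions of cladribine and cytarabine are to be considered, with no size given.
- **Appendix B.** The doses of 6.8.1 appear as the first reduction level, including "Mitoxantrone 14 mg/m ²", under the introduction "the following dose reduction can be considered for the next course".
- **Re-induction (6.5.3).** A patient with persistent disease may have a second induction course at the dosing of the first. The Study Overview in 6.0 also says re-induction uses the same dosing.

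**The concern.** The toxicity step is written as absolute doses that fit a patient who started at full dose. Sections 6.3.6 and 6.8.2 create another kind of patient, whose first course was already reduced for bilirubin. Neither 6.8.1 nor Appendix B mentions the dose actually given, so a step meant to lower exposure can, on its literal wording, raise it.

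The sequence is one the text allows. Section 6.8 names baseline organ dysfunction and first-induction toxicity as its two triggers, and one patient can meet both. Eligibility (3.1, 3.2) sets no bilirubin or creatinine limit.

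At stake is the safety of the individual patient at the second induction course. Delivered intensity would also depend on which paragraph the treating physician follows. The primary endpoint, willingness to be randomized, is not affected.

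**Working it through.** The documents give no formula for 14 mg/m², so there is no derived figure to reproduce. Section 6.8.1 and Appendix B agree on the value.

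**Inputs.** Full dose 18 mg/m² (6.3.1); bilirubin reduction r = 25% to 50% (6.8.2); dose after toxicity 14 mg/m² (6.8.1, Appendix B); three dosing days.

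**Step 1. First-course dose after the bilirubin reduction: 18 x (1 - r).**

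| r | First-course dose (mg/m²/day) | 14 minus this dose | 14 / dose - 1 | Course total, 3 days | Total at 14 mg/m² |
|---|---|---|---|---|---|
| 25% | 18 x 0.75 = 13.5 | +0.5 | +3.7% | 40.5 | 42 |
| 50% | 18 x 0.50 = 9.0 | +5.0 | +55.6% | 27 | 42 |

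**Step 2. Where the sign changes.** The step from 18 to 14 is a cut of 1 - 14/18 = 22.2%. Any earlier cut larger than 22.2% makes 14 mg/m² an increase. The smallest cut named in 6.8.2 is 25%, so the reversal holds over the whole range.

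**Step 3. What each passage implies for this patient's second G-CLAM course.**

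| Passage | Mitoxantrone implied (mg/m²/day) |
|---|---|
| 6.5.3, first-course dosing repeated | 9-13.5 |
| 6.8.1, taken literally | 14 |
| 6.8.2 applied again, percentage taken from 18 | 9-13.5 |
| 6.8.2 applied again, percentage taken from 14 | 14 x 0.50 = 7 to 14 x 0.75 = 10.5 |
| 6.8 lead-in and Appendix B, optional reduction | not determined |

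The text does not rank these passages or say which base the percentage uses.

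**Step 4. Cladribine and cytarabine.** The 6.8.1 steps are 1 - 4/5 = 20% and 1 - 1,500/2,000 = 25%. The same reversal would need an earlier renal cut above 20% for cladribine or above 25% for cytarabine. Sections 6.8.3 and 6.8.4 give no sizes, so this part is conditional.

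**The case against.** The strongest reply is that 6.8.1 should be read under its heading. The lead-in to 6.8 makes the step optional and calls it a reduction, and so does Appendix B; 6.8.2 itself only asks that a cut be considered. An increase is not a reduction, organ-function cuts go through the Oncology Pharmacist, and a sensible physician would probably not escalate. This stands as evidence that no increase is intended. It does not settle the wording: 6.8.1 states its doses in mandatory terms, and a rule meant to reduce dose should not have to be disregarded to avoid raising it.

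It is also fair that few patients are involved. Each must be on the higher-dose arm, have baseline bilirubin at least 3 x IULN, receive the optional cut, have qualifying toxicity, recover, and then have a second G-CLAM induction, in a study of up to 50. At a 25% cut the difference is only 0.5 mg/m².

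A reader might infer more, but the documents do not support it:

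- *That the 22.2% step contradicts the 25-50% range.* The two rules have different triggers, toxicity and bilirubin, so their sizes need not match. What is missing is how they combine.
- *That the missing second mitoxantrone level in Appendix B is a gap.* The higher-dose arm allows at most two G-CLAM courses, and consolidation omits mitoxantrone, so there is no later mitoxantrone dose to reduce.
- *That the early-death rules watch this arm most closely or would be distorted.* In 14.4 the within-arm rule is the same for both arms and counts deaths to day 28. A second course follows marrow reassessment at count recovery or days 28-35, so it falls largely outside that window.
- *That sites would differ.* The study is single-center (6.0); any variation would be between physicians.
- *That the creatinine term in the TRM score makes the case common.* The computed reversal is driven by bilirubin, which is not in the score.

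**Conclusion.** The point holds as an unresolved conflict in the dose-modification text. For every reduction that 6.8.2 names, the literal dose in 6.8.1 is above the one that preceded the toxicity: by 3.7% after a 25% cut and by 55.6% after a 50% cut. No other passage resolves this. The lead-in and Appendix B differ from 6.8.1 on whether the step is optional, and 6.5.3 points to the first-course dosing without saying whether 6.8.1 overrides it.

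The conclusion assumes that the bilirubin cut was taken from 18 mg/m² at the first course, within 25-50%, and that 6.8.1 is applied as worded. It does not show that the protocol intends to escalate after toxicity. The number affected cannot be computed from the documents and is probably small. The extension to cladribine and cytarabine remains conditional. The point merits correction because a stated safety rule can give a result contrary to its own purpose.

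**What to change.** Reconcile 6.3.6, 6.5.3, 6.8 (lead-in and 6.8.1-6.8.4) and Appendix B so that together they give one instruction for a patient whose previous course was already reduced. The text should say:

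1. whether 6.8.1 is mandatory or optional;
2. how its fixed doses apply after a reduced course;
3. which passage governs when the organ-function and toxicity triggers are both met, and from which dose any percentage is taken;
4. how 6.8.1 relates to the re-induction dosing in 6.5.3.

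The clinical team decides the doses and the rule; this review proposes neither. The cost is a few sentences of protocol wording and a footnote to Appendix B, with no added patients, visits or procedures.
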